12.3.7.5 Anti-drug antibodies

ADA status (positive versus negative) at each visit will be summarised by treatment group for initial, maintenance and open-label treatment. If considered relevant, descriptive statistics including number of subjects, mean, standard deviation, median, and range of the actual ADA titres by treatment group and visit will be provided. The ADA status across the trial for each subject (positive versus negative) will also be classified and summarised by treatment group.

The association of ADA status across the trial (positive vs. negative) with AEs/SAEs may be evaluated. In addition, the association of ADA titres (\geq median titre in positive subjects versus < median titre) with AE/SAEs may be evaluated for ADA-positive treated subjects only. The

Trial ID: LP0162-1325	Date: 14-Aug-2018	Version: 4.0
		Page 113 of 169

ADA-positive subjects across the trial may also be divided into persistent positive versus transient positive. A subject will be considered as persistent positive if he/she has positive ADA for at least 2 consecutive visits with ADA assessment. Otherwise, the subject will be considered as transient ADA positive. The associations between ADA and AE/SAEs may be summarised for both persistent positive subjects versus transient positives subjects.

For subjects who develop ADA, the IGA score and change in EASI at end of treatment will be listed.

Evaluations of nAB will be conducted on those serum samples that test positive for ADA. The test sample is deemed positive or negative for the presence of nAb to tralokinumab relative to a pre-determined (in assay validation), statistically derived cut point.

For ADA, all subjects with titre information will be listed.

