3) Assessments performed at Week 16 are also to be done at an early termination visit and at a nominal Week 16 visit, if applicable. See Section 8.5 for further details. All subjects will have a final safety follow-up (FU1) 16 weeks after the last dose of IMP, except subjects who enter the long-term extension trial (conducted under a separate protocol [LP0162-1337, ECZTEND]). Subjects may enter ECZTEND at any time during the safety follow-up period (see Section 7.1). An end of treatment form and end of trial form must be completed in the eCRF for all subjects assigned treatment.

Trial ID: LP0162-1325	Date: 14-Aug-2018	Version: 4.0
		Page 21 of 169

- 4) Additional informed consents are required for participation in (i) the exploratory component involving microbiome skin swab, large biomarker panel, and skin biopsy, and (ii) the photograph component (selected trial sites only).
- 5) Subjects who are eligible for home-use during open-label treatment will have to provide additional informed consent before the training at the site (Section 9.2); home-use will only commence after proper training of the subject or caregiver (at 3 dosing visits after the additional consent has been obtained) and after 3 doses of open-label tralokinumab administered at the trial site, i.e., starting no earlier than Week 22, depending on when the subject transfers to open-label treatment (selected countries only).
- 6) All subjects must use an emollient twice daily (or more, as needed) for at least 14 days before randomisation and must continue this treatment throughout the trial.
- 7) Subjects who achieve a clinical response (IGA 0/1 or EASI75) at Week 16 will be re-randomised into the maintenance period and then receive the first injections of maintenance treatment (Panel 3). Subjects that do not achieve clinical response at Week 16 will be transferred to open-label tralokinumab 300 mg Q2W treatment with optional use of TCS and then receive the first injections of open-label treatment (Panel 4).
- 8) For the first 3 IMP dosing visits in both the initial and open-label treatment period, subjects will be monitored after IMP administration for immediate drug reactions for a minimum of 2 hours with vital signs taken every 30 minutes or until stable, whichever is later (Section 9.2).

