Subjects transferring to open-label treatment will have the option to self-administer tralokinumab – or have tralokinumab administered by a caregiver – in their home after adequate training by site staff at the investigator's discretion (Section 9.2). This home-use will only commence after 3 doses of tralokinumab have been administered at the trial site (i.e., starting no earlier than Week 22, depending on when the subject transferred to open-label) as a safety precaution for subjects receiving their first active therapy. After proper training of the subject and/or the caregiver that is, at 3 or more dosing visits during open-label treatment after additional consent for home-use has been obtained, these subjects will only have trial visits every 4 weeks. For subjects where home-use is inappropriate, tralokinumab will continue to be administered by site staff at the trial visit.

Short-term extension (Week 52 to Week 68)

For selected countries

Subjects who join the open-label tralokinumab arm at Week 16 will continue an additional 16 weeks of open-label treatment in order to secure at least 52 weeks of active therapy.

Safety follow-up period (Week 52 to Week 66 [or Week 68 to Week 82])

All subjects, except for those who enter the long-term extension trial (LP0162-1337, ECZTEND, see below), will complete a 14-week off-treatment follow-up period for the assessment of safety and ADA at Week 66 (or Week 82).

Trial ID: LP0162-1325	Date: 14-Aug-2018	Version: 4.0
		Page 43 of 169

Long-term extension trial

Eligible subjects may be invited to enter a long-term extension trial conducted under a separate protocol (LP0162-1337, ECZTEND). Subjects who transfer to ECZTEND must have had their last visit in the treatment period (Week 52 or Week 68 [*selected countries*]) under the current protocol (LP0162-1325).

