10.4.7 Anti-drug antibodies measurements

Blood samples will be collected for determination of anti-tralokinumab antibody levels at pre-determined time points according to the SoP (Section 4).

Collection, handling and shipment instructions for ADA blood samples are provided in a separate laboratory manual.

Serum samples for determination of presence or absence ADA will be analysed by a laboratory using a validated bioanalytical method. A tiered testing scheme will be employed, with the first step being screening. Samples found positive in the screening step will be tested in the confirmatory step. Samples confirmed positive for ADA in the confirmatory step will undergo ADA endpoint titre determination and will be analysed for the presence of

Trial ID: LP0162-1325	Date: 14-Aug-2018	Version: 4.0
		Page 79 of 169

neutralising antibodies (nAB). Details of the analytical method used will be described in the ADA bioanalytical report.

Samples will be retained for as long as the quality of the material permits evaluation but for no longer than 15 years after marketing authorisation.

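### A subject whose only positive ADA result is the last available sample is labelled transient, although resolution was never observed

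*Protocol*

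**What the plan says.** Protocol Section 12.3.7.5 makes the split optional: "ADA-positive subjects across the trial may also be divided into persistent positive versus transient positive". The rule for the first class is: "A subject will be considered as persistent positive if he/she has positive ADA for at least 2 consecutive visits with ADA assessment". The second class is whatever remains: "Otherwise, the subject will be considered as transient ADA positive". The intended use is also optional: "The associations between ADA and AE/SAEs may be summarised for both persistent positive subjects versus transient positives subjects".

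The ADA rows of the schedule of procedures (Protocol Section 4) give Weeks 0, 4 and 16 in Panel 2, then Weeks 28, 52 and 66 (FU1) in Panels 3 and 4. Panel 5, for the short-term extension in selected countries, adds Weeks 68 and 82 (FU2).

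Not everyone has the off-treatment sample. Section 7.1 states: "All subjects, except for those who enter the long-term extension trial (LP0162-1337, ECZTEND, see below), will complete a 14-week off-treatment follow-up period". Footnote 3 to Panel 2 in Section 4 adds: "Subjects may enter ECZTEND at any time during the safety follow-up period". Section 7.3 counts subjects who take this route after Week 52 or Week 68 as trial completers.

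SAP Section 6.7.7 covers ADA in one sentence that promises summaries and listings. It neither redefines the two classes nor deals with a positive final sample.

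**The concern.** Transient describes a course over time: the antibody was detected and later was not. The plan assigns the label without asking for the second observation. A subject with one positive result at the end of sampling may have an antibody that would have persisted or one that would have disappeared, and the data cannot tell which.

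The schedule gives room for this. Later ADA samples are far apart, and the extension route can remove the one sample that could confirm or refute a positive at Week 52. The main report is exposed as well. Under Protocol Section 12.3.9 it uses a cut-off at the last subject's Week 52 visit, with final follow-up results in an addendum. A subject whose follow-up sample falls after the cut-off could be transient in the report and persistent in the addendum.

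At stake is the meaning of an optional table that sets adverse events in persistent subjects beside those in transient subjects. If the transient column mixes resolved with undetermined cases, the contrast no longer describes what its labels say.

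**Working it through.** The plan states no figure for this split, and it gives no ADA rate, no timing of seroconversion and no rate of entry to the extension trial. There is nothing to reproduce, so the check applies the rule to the schedule.

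**Step 1: the rule on each schedule.** Every positive/negative pattern was classified: persistent if any two adjacent assessed samples are positive, otherwise transient if any sample is positive.

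| Scheduled ADA samples (weeks) | Label when only the last is positive | Patterns labelled transient | Of these, ending on a positive |
|---|---|---|---|
| 0, 4, 16, 28, 52, 66 | transient | 20 | 8 |
| 0, 4, 16, 28, 52 | transient | 12 | 5 |
| 0, 4, 16, 28, 52, 68, 82 | transient | 33 | 13 |
| 0, 4 (lost after Week 4) | transient | 2 | 1 |

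These are counts of possible patterns, not expected shares of subjects. In each row exactly one pattern ending on a positive has no earlier positive. The other 7, 4, 12 and 0 have an earlier isolated positive followed by a negative, so a resolution was seen at least once.

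**Step 2: last sample at Week 52.** The previous scheduled sample is Week 28, a gap of 52 − 28 = 24 weeks. A first positive at Week 52 means Week 28 was negative, so two adjacent positives are impossible and the label must be transient. In the short-term extension there is a further sample at Week 68. A subject first positive at Week 52 and still positive at Week 68 is persistent, and the problem moves to first positives at the later final sample.

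**Step 3: size, by assumption.** Assume antibodies never resolve, no sample is missed and the last sample is Week 52. Anyone who seroconverts by Week 28 is then positive at two adjacent visits and is persistent. Anyone who seroconverts later is positive at Week 52 only and is called transient. The mislabelled share is therefore s, the share of seroconversions after Week 28.

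- All onset by Week 28: s = 0%.
- 10% of onsets after Week 28: s = 10%.
- Onset uniform over Weeks 0 to 52: s = 24/52 = 46%.

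For short-term extension subjects last sampled at Week 68, the same reasoning with uniform onset over 68 weeks gives (68 − 52)/68 = 16/68 = 24%. Uniform onset from Week 0 does not fit subjects initially on placebo, who receive no tralokinumab before Week 16.

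**The case against.** The strongest reply is that little depends on the label. The protocol says only that the split and the adverse-event summary may be produced. No hypothesis, significance level or confirmatory endpoint is attached. ADA status is summarised at each visit and subjects with titre information are listed, so last-sample positives can be traced. All of this stands and keeps the point minor. It does not make the label correct where it is used.

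A reader might infer more than the documents support:

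- **That the ADA-frequency endpoint is distorted.** It is not. Frequency rests on positive or negative status, and dividing the positives leaves it unchanged.
- **That extension entrants in general can never be persistent.** This holds only for those first positive at Week 52 with no later sample. Those positive at both Weeks 28 and 52 are persistent, and short-term extension subjects also have Week 68.
- **That 46% of positives would be mislabelled.** That figure follows from one assumed onset pattern combined with no resolution. The documents give nothing to choose it over 0%.
- **That persistence is understated or an association with adverse events diluted.** A single final positive is undetermined, and the direction of any effect is not shown.
- **That a subject positive only at Week 0 is certainly counted as transient.** Section 12.3.7.5 does not say whether a pre-dose positive counts towards status across the trial, and it refers to subjects who develop ADA without defining this. It is a separate ambiguity: such a subject, negative afterwards, would also meet a rule requiring a later negative sample.

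**Conclusion.** The point holds as a minor defect of definition. Read literally, Section 12.3.7.5 labels a last-sample-only positive as transient on every schedule in the protocol, and the SAP does not repair it. This is a stated rule that gives an unsupported label, rather than a detail left out.

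The number of subjects affected cannot be computed. For those last sampled at Week 52, and assuming no resolution, it is the share of seroconversions after Week 28: 0% if all occur earlier and 46% if onset is uniform over 52 weeks. The consequence is confined to the optional persistent-versus-transient summary, including its use with adverse events, where resolved and undetermined cases would be mixed.

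**What to change.** In the SAP, if the split is used:

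1. Call a subject transient only if a positive sample is followed by at least one negative sample and the persistent rule is not met.
2. Report subjects whose only positive is the last available sample as a separate undetermined category. Alternatively, show the table twice, with these subjects counted each way.
3. Separately, state that a pre-dose Week 0 positive alone does not count as treatment-emergent ADA.

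No new data or sampling is needed. The cost is a few lines of SAP wording and one extra table category, best settled before the randomisation code is broken.

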Safety assessments (Sections 10.4 and 11))																		
Vital signs	Х	X	Х	Х	Х	Х	X	x	Х	Х	X	Х	х	X	Х	Х	Х	Х	Х
Physical examination								x								Х		х	х
ECG				Х				х				Х				Х		х	х
Urine pregnancy test		х		х		х		х		х		х		х		х		х	х

Trial ID: LP0162-1325	Date: 14-Aug-2018	Version: 4.0
		Page 23 of 169

Panel 3 Schedule of trial procedures: maintenance treatment period and follow-up (continued)

							N	[ainten	ance tr	eatme	nt perio	bd							FU1 ²
Visit	13	14	15	16	17	18	19	20	21	22	23	24	25	26	27	28	29	30 ¹	31
Week	18	20	22	24	26	28	30	32	34	36	38	40	42	44	46	48	50	52	66
Safety assessments (Sections 10.4 and 11))																		
Serum chemistry, haematology, and IgE		х		Х		х		х		х		х		Х		х		х	Х
Urinalysis				Х				Х				Х				Х		Х	Х
Pharmacokinetics						х												х	Х
ADA						х												х	Х
Adverse events	Х	Х	Х	Х	Х	Х	Х	Х	Х	Х	X	Х	Х	Х	Х	Х	Х	Х	Х
Other assessments (Section 10.5)																			
Skin swabs (S. aureus)																		х	
Skin swabs (microbiome) ⁵																		Х	
Serum biomarkers (small panel)						х												х	
Serum biomarkers (large panel) ⁵						х												х	
Photography ⁵		х		х		х		х		х		х		х		х		х	

1) Assessments also to be done at an early termination visit.

2) Subjects will have a safety follow-up (FU1) 16 weeks after last injection of IMP; this is considered the end of trial visit. For subjects who are enrolled into the long-term extension trial (conducted under a separate protocol [LP0162-1337, ECZTEND]), the end of trial visit will be the last visit in trial LP0162-1325 before transfer to the extension.

- 3) Subjects who meet the following criteria will be transferred to open-label treatment (tralokinumab 300 mg Q2W with optional use of TCS [Panel 4]):
 - Subjects with IGA=0 at Week 16: IGA of at least 2 and not achieving EASI75 over at least a 4-week period (i.e., over 3 consecutive visits).
 - Subjects with IGA=1 at Week 16: IGA of at least 3 and not achieving EASI75 over at least a 4-week period (i.e., over 3 consecutive visits).
 - Subjects with IGA >1 at Week 16: not achieving EASI75 over at least a 4-week period (i.e., over 3 consecutive visits).

The first injections of open-label treatment will be given at the visit in the maintenance period where the subject meets these criteria.

Trial ID: LP0162-1325	Date: 14-Aug-2018	Version: 4.0
		Page 24 of 169

4) The eDiary consists of (i) Eczema-related Sleep NRS, (ii) Worst Daily Pruritus NRS, (iii) Average Daily Pruritus NRS, (iv) PGI-B, and (v) PGI-S.

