8.5 Discontinuation

A subject may withdraw from trial or from treatment at any time (prior to first dose or during treatment period) at his/her own request. A subject may be withdrawn at any time at the discretion of the investigator. Discontinued subjects will not be replaced.

Medical reasons for permanent discontinuation of IMP are given in Section 9.8.1.

Assessments

Subjects who permanently discontinue IMP for any reason will be asked to attend an early termination visit and return to the trial site for 1 or 2 additional visits as indicated below depending on the time of discontinuation of IMP (see the SoP [Section 4] for data to be collected at these visits). The investigator will review any AEs which will be followed-up according to Section 11.6, if the subject agrees.

Subjects who permanently discontinue IMP prior to Week 16 will be asked to attend:

- Early termination visit.
- Nominal Week 16 visit (16 weeks after randomisation).
- Safety follow-up visit (16 weeks after last administration of IMP).

Subjects who permanently discontinue IMP at Week 16 or after Week 16 will be asked to attend:

- Early termination visit.
- Safety follow-up visit (16 weeks after last administration of IMP).

If a subject withdraws from the trial, he/she may request destruction of any samples taken and not tested, and the investigator must document this in the site's trial records.

Reason(s) for discontinuation from IMP and withdrawal from the trial must be recorded in the medical records and the eCRF (lack of efficacy, AE, withdrawal by subject, lost to follow-up, death, other). For subjects randomised to IMP but not attending any post-baseline visits, it will be recorded whether any safety evaluations were performed after exposure to IMP.

Lost to follow-up

A subject will be considered lost to follow-up if they repeatedly fail to return for scheduled visits and if the trial site is not able to get in contact with the subject.

The following actions must be taken if a subject fails to return to the trial site for a required visit:

- The trial site must attempt to contact the subject and reschedule the missed visit as soon as possible and counsel the subject on the importance of maintaining the assigned visit schedule and ascertain whether or not the subject wishes to and/or should continue in the trial.

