12.3.9 Analysis of data per last subject's Week 52 visit

To support submission for regulatory approval, the trial will be unblinded once all randomised subjects have completed the Week 52 visit. All pre-specified analyses related to the initial and maintenance treatment period will be based on the data cut-off date of the last subject's Week 52 visit. The CTR will include all data from all randomised subjects from the initial and maintenance treatment period and all available data from the open-label treatment period and safety follow-up period as per data cut-off date.

Once all subjects have completed the open-label treatment period and safety follow-up period, an addendum to the original CTR will be written, summarising the final results from the open-label treatment period and safety follow-up period.

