## 6.7.7 Pharmacokinetics and anti-drug antibodies

Pharmacokinetics and anti-drug antibodies data will be summarised and listed.

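### The optional persistent/transient ADA split calls a subject 'transient' even when the only positive sample is the last one taken

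*Protocol*

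**What the plan says.** Protocol 12.3.7.5 sets the rule in two sentences. First: "A subject will be considered as persistent positive if he/she has positive ADA for at least 2 consecutive visits with ADA assessment". Then, for all other ADA-positive subjects: "Otherwise, the subject will be considered as transient ADA positive". The section says that the split may be made and that AEs and SAEs may be summarised by it. Neither is a firm commitment. The firm outputs are ADA status by visit, positive or negative status across the trial, and a listing of titres.

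The schedule panels in Protocol Section 4 place ADA samples at Weeks 0, 4 and 16 (Panel 2), Weeks 28, 52 and 66 (Panels 3 and 4), and Weeks 68 and 82 in the short-term extension (Panel 5). Week 66 is FU1 and Week 82 is FU2.

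Not everyone gives the follow-up sample. Protocol 7.1 states: "All subjects, except for those who enter the long-term extension trial (LP0162-1337, ECZTEND, see below), will complete a 14-week off-treatment follow-up period". Footnote 3 of Panel 2 lets subjects move to ECZTEND at any point during follow-up.

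SAP 6.7.7 leaves the rule unchanged. Its whole text is: "Pharmacokinetics and anti-drug antibodies data will be summarised and listed".

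**The concern.** Transient suggests that antibodies appeared and then went away. Under the rule it also covers a subject who was negative until the last sample and positive on it. For that subject the data show neither loss nor persistence, and the rule chooses transient by default.

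The schedule makes this more than a remote case. The gap between the Week 28 and Week 52 samples is long, and for subjects who go straight into ECZTEND no scheduled sample follows in this trial. If the split is produced as written, some subjects who were ADA-positive when last sampled will be reported as having transient ADA, and persistence will be understated to that extent. Frequency of ADA is a listed endpoint for both treatment periods (Protocol 6.1 and 6.2), so readers can be expected to look at these tables.

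**Working it through.** The plan gives no figure for this point, so there is none to reproduce. The check applies the rule to the sampling schedule.

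**Inputs.** The rule is in Protocol 12.3.7.5. The sampling weeks are in Panels 2 to 5. The possible last samples are in Protocol 7.1 and the panel footnotes.

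**Step 1. Schedule by follow-up path.**
- ECZTEND directly after Week 52: Weeks 0, 4, 16, 28, 52
- FU1: Weeks 0, 4, 16, 28, 52, 66
- Short-term extension, then ECZTEND at Week 68: Weeks 0, 4, 16, 28, 52, 68
- Short-term extension, then FU2: Weeks 0, 4, 16, 28, 52, 68, 82

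**Step 2. Apply the rule to ADA that starts in a given interval and lasts** (0 = negative, 1 = positive), with direct ECZTEND entry after Week 52:
- First positive at Week 4: 0,1,1,1,1, persistent
- First positive at Week 16: 0,0,1,1,1, persistent
- First positive at Week 28: 0,0,0,1,1, persistent
- First positive at Week 52: 0,0,0,0,1, transient

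Only the last pattern is affected. On every path it is the one in which the final sample is the first positive.

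**Step 3. Length of the affected window** = last sample minus the one before it.
- ECZTEND after Week 52: 52 − 28 = 24 weeks
- FU1: 66 − 52 = 14 weeks
- ECZTEND at Week 68: 68 − 52 = 16 weeks
- FU2: 82 − 68 = 14 weeks

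**Step 4. Why the wording must be 'first positive after Week 28'.** With five samples, eight patterns are negative at Week 28 and positive at Week 52. Three are already persistent through earlier consecutive positives (0,1,1,0,1; 1,1,0,0,1; 1,1,1,0,1). The other five are labelled transient: 0,0,0,0,1, and four with one or two isolated earlier positives. All five end on a positive sample.

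**Step 5. Same course, different path.** Take ADA that starts at Week 40 and lasts.
- Direct ECZTEND entry after Week 52: one positive, transient.
- FU1 attended: positive at Weeks 52 and 66, persistent.
- IMP stopped after the Week 44 dose: positive at the early-termination visit (Panel 3, footnote 1: "Assessments also to be done at an early termination visit") and at the follow-up visit 16 weeks after the last dose (Protocol 8.5), persistent if both are attended.

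**Step 6. Cut-off.** Protocol 12.3.9 bases the clinical trial report on "all available data from the open-label treatment period and safety follow-up period as per data cut-off date". A subject with 0,0,0,0,1 and Week 66 still pending is transient in the report, and becomes persistent in the addendum if Week 66 is positive.

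**The case against.** The strongest reply is that almost nothing rests on this. The split and the AE summary by it are both optional, the definition is explicit and reproducible, and the firm outputs do not use it. A lone Week 52 positive can be recognised from the visit-level results. All of this stands, and it keeps the point minor.

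A second reply is that the protocol accepted the loss of the follow-up sample on purpose. Its amendment summary explains that the new assay detects ADA with drug present, and that ECZTEND entrants have their follow-up after treatment ends in that trial. This stands as a reason for dropping the visit. But a readable Week 52 result is still one result, and whether ECZTEND supplies later ADA data cannot be seen from these documents. An ADA sample at an unscheduled visit is possible under Protocol 10.1 but not planned.

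A reader might infer three stronger things that the documents do not support.
- **That the label depends on extension entry rather than on the ADA course.** It does not for early converters: lasting ADA first positive by Week 28 is persistent on every path in Step 1.
- **That stopping IMP, for example for an AE, in itself favours the persistent label.** In Step 5 this holds only against direct ECZTEND entrants. The FU1 attendee is also persistent, and the subject who stops must attend the follow-up visit.
- **That a given share or number of subjects is mislabelled.** This would need ADA incidence, the timing of conversion, how long ADA lasts and the rate of extension entry. None is given, so any count would be assumption.

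**Conclusion.** The point holds as a small improvement. The rule gives a label that the data cannot support to a subject with no two consecutive positives whose last available sample is positive. For direct entry to ECZTEND after Week 52, that includes everyone first positive after Week 28 (a 24-week window). On the other paths the window is 14 to 16 weeks and falls later. These windows follow from the schedule alone and assume that only scheduled samples are taken.

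The direction is known: where it occurs, persistence is understated. The size in subjects is not known and cannot be derived from the documents. If conversion is mostly early, few or no subjects are affected. No hypothesis test, firm ADA output or efficacy result changes.

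**What to change.** Add to SAP 6.7.7, to apply if ADA-positive subjects are divided:
- persistent: positive at two or more consecutive ADA visits
- transient: no two consecutive positives, and last available ADA sample negative
- undetermined: no two consecutive positives, and last available ADA sample positive

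The three groups are exclusive and cover every ADA-positive subject. The definition of persistent is unchanged. The five transient patterns in Step 4 become undetermined.

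The change stops subjects who were positive when last sampled from being reported as transient. It does not make labels identical across paths: the Week 40 converter would be undetermined with direct ECZTEND entry and persistent with FU1. Nor does it freeze labels at the cut-off. An undetermined subject may become persistent or transient in the addendum once Week 66 arrives, which is ordinary updating.

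The cost is one sentence and one flag derived from the visit-level ADA results already planned. It needs no new data and affects no test. The downside is a small third group, and a smaller transient group, in an optional table.
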